D2I. Performing the study at the pilot stage in Israel is optimal - [name], the Asaf Harofeh site PI , is the chairman of the Israeli Society for Hyperbaric & Diving Medicine and an internationally renowned leader in HBOT. The Asaf Harofeh Hyperbaric Unit is one of the largest, most active worldwide with about 100 patients treated per day, in a variety of FDA approved indications (e.g. non-healing ischemic wounds, post radiation injury, chronic osteomyelitis). *There is widespread accessibility of HBOT chambers in the US (please see letter of support from [name], the American Undersea & Hyperbaric Medical Society Executive Director describing ~1400 US HBOT chambers, with an estimated annual growth of 8-10%). This suggests that finding collaborative HBOT facilities in the US would not be a problem in a large-scale multi-center RCT for cognitively impaired T2D patients based on this pilot study.* Importantly, the typical US cost of HBOT treatment is significantly higher than in Israel, making the proposed pilot study sample size feasible within the current funding mechanism. The Sheba Medical Center is the largest hospital in the Middle East, and is home for the NIH funded IDCD study, so it has all the necessary infrastructure, personnel, experience, and expertise in recruitment of elderly subjects with T2D, and of assessment of the cognitive and biological outcome measures of the proposed study. It is only 8 miles from Asaf Harofeh, facilitating visits by subjects who will be primarily from the Tel-Aviv area encompassing both hospitals. The professional staff is of superb quality but at significantly lower cost than in the US. Finally, subjects will be recruited through talks in the community, advertisements, and companies which have large lists of elderly interested in receiving emails about health related topics. Medical information will be given us by the subject.

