D6. Statistical Analysis Plan- Efficacy analyses will be performed for the intent-to-treat (ITT) population, our primary analysis, and for fully and partially compliant per-protocol (PP) populations. The ITT population will include all participants in the group to which they were randomized, regardless of any protocol deviation including non-compliance, adverse events, or loss of follow-up. The PP populations will include participants in the group according to the intervention actually received, but a separate analysis will be performed for those who were fully compliant (at least 80% of sessions completed) and for those who were partially compliant (at least one session completed). A complier-average causal effect (CACE) analysis using a latent class modeling approach will also be performed on both fully and partially compliant populations. Patients missing a baseline value of a continuous efficacy outcome measure will be excluded from all analyses and maximum likelihood estimation methods will be used to handle missing data arising from an unobserved follow-up visit¹²².

Aims 1a and 1b: The primary (overall cognition) and secondary (executive functions, episodic memory domains, and computer-based tests) cognitive outcome measures (all summaries of z-scores), will each be analyzed using a mixed model analysis of covariance (ANCOVA) with time of assessment (baseline or 12 weeks) as the within-subjects factor, treatment group (HBOT vs. sham) as the between-subjects factor and baseline value of the outcome measure as the covariate. *Both, subject and 'cluster' (the variable used to identify to which group of at least 3 subjects each individual is assigned) will be modeled as random effects to account for the correlation among repeated measurements made over time within a subject as well as potential 'cluster effects' arising from blocks of at least 3 patients receiving treatment at a particular time after randomization.* An interaction term between time of assessment and treatment group will be included in each model allowing for estimation of the mean change from baseline to 12 weeks in each treatment group as well as a test for difference

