in change scores between groups. A test of parallel treatment effects across the range of baseline values will be conducted by including a three-way interaction term among time of assessment, treatment group and baseline value of the outcome variable as well as all lower order two-way interaction terms. If the three-way interaction term is statistically significant it will be retained in the final model and estimates of the difference in mean change scores between treatment groups will be evaluated at selected percentiles of the baseline distribution. Secondary mixed model ANCOVA analyses will be performed for cognitive assessments at 6 and 12 months following treatment. As an exploratory analysis, linear mixed effects models will assess the relationship between treatment group (fixed effect) and the longitudinal trend (random intercept and slope for each subject) in the primary and secondary cognitive outcome measures, assessed at 12-weeks, 6 months and 12 months following treatment. The primary hypothesis will be tested by assessing the interaction between treatment group and time of cognitive follow-up assessment, with a significant interaction indicating a difference in longitudinal cognitive trends between treatment groups. Potential confounders (age, gender, education, *duration of T2D, HbA1c, diabetes medications [insulin vs. no medications and oral agents vs. no medication], levels of atrophy and white matter hyperintensities*) will be included as covariates if there is imbalance at baseline ($p<0.1$) or association between the covariate and the response ($p<0.15$).

To explore whether specific dichotomized T2D characteristics (such as the last HbA1c level (dichotomized at 7) in the Diabetes Registry, the number of T2D complications, and the number of severe hypoglycemic episodes in the year preceding randomization) are associated with greater improvements following treatment with HBOT, mixed effects ANCOVA models similar to those for Aims 1 and 2 will add a main effect for the specific T2D characteristic and an interaction term between treatment group and the characteristic. Using the MHS dataset, we will also explore associations of dosage of the most prevalently used medications with cognitive outcomes. When potential confounders are associated with cognitive outcomes, this also may identify subgroups for which HBOT is particularly effective.

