Aim 1. Power is presented for detecting the difference in mean change (from baseline to 12 weeks) in overall cognition z-scores between the sham and HBOT treatment groups. Power calculations are based on two-sample t-tests and are conducted with a 2-sided 5% significance level (**Table 3**). A 2-sample t-test provides a more conservative power estimate than the proposed mixed model approach, which is expected to explain more variability and thus have more power to detect the same effect size with the same sample size.

The predicted mean change in the sham group from baseline to 12 weeks is -0.02 (based on the IDCD 12-week change in overall cognition). Assuming an SD of 0.50 in both the sham and HBOT groups, with a minimum sample size of 67 patients per arm, we have 80% power to detect an improvement in the HBOT group of 0.224, a “medium” effect size of 0.49. To account for an anticipated dropout rate of 13% (a reasonable estimate compared to the 5% dropout rate in our stroke study), we plan to enroll 77 patients per group for a total of 154 patients. Our HBOT trial years after mild traumatic brain injury⁷⁴ had an effect size of 0.47 for information speed processing which is clinically comparable to our primary outcome measure of overall cognition, and our HBOT trial on stroke patients⁷⁸ showed an effect size of 0.49 for the National Institutes of Health stroke scale, suggesting our detectable effect size of 0.49 is feasible.

Aim 2: As for Aim 1, power is presented for detecting the difference in the mean changes in CBF velocity and cerebral glucose utilization between the Sham and HBOT groups. Assuming a mean change in CBF velocity of -0.45 in the Sham group and an SD of 5.6 in both groups, with a minimum sample size of 67 patients per arm we have 80% power to detect an improvement in the HBOT group of 2.28, an effect size of 0.49. *To account for an anticipated dropout rate of 13%, we plan to enroll 77 patients per group for a total of 154 patients.* For cerebral glucose utilization, assuming a mean change in the sham group of -0.08 and an SD of 4.40 in both groups, with

Table 3: Two group t-test of equal means, equal n's)*			
	Outcome		
	Overall Cognition z-score	CBFV [†]	CGU [‡]
Sham Mean Change, D ₁	-0.020	-0.450	-0.08
HBOT Mean Change, D ₂	0.224	2.28	2.065
Difference in means, D ₁ -D ₂	-0.244	-2.73	-2.145
HBOT SD	0.50	5.60	4.40
Minimum N per group	67	67	67
Enrollment N per group**	77	77	77

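### Fitted as written, the D6 subgroup model has no term for effect modification of change, and its treatment-by-characteristic coefficient is about half the true size

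*Combined protocol and SAP*

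**What the plan says.** In D6 (Aims 1a and 1b), the cognitive outcomes are analysed by a mixed-model ANCOVA "with time of assessment (baseline or 12 weeks) as the within-subjects factor", with treatment group between subjects and the baseline value as covariate. The treatment effect is the time x treatment interaction, which D6 describes as giving the change in each arm and the test of the difference in change.

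To check whether the treatment effect depends on the baseline value, D6 writes out a three-way interaction of time, treatment and baseline value, together with the lower-order two-way terms.

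For the T2D characteristics, D6 asks whether they go with larger gains after HBOT. It says that models like those of Aims 1 and 2 "will add a main effect for the specific T2D characteristic and an interaction term between treatment group and the characteristic". No term involving time is named. The characteristics are dichotomised, and three examples are given. One is "the last HbA1c level (dichotomized at 7) in the Diabetes Registry".

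On data sources, D2I says "Medical information will be given us by the subject". Section E.1.a has participants supply their HMO computerised chart, including HbA1c. D2K names haemoglobin A1c among the diabetes markers in trial blood, and Table 2 schedules a baseline blood test.

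**The concern.** The question is about improvement, and in this model improvement by treatment is time x treatment. A characteristic can modify that only through time x treatment x characteristic. Without it, the fitted difference in change between arms is the same in both subgroups by construction, and no parameter answers the question. An analyst would then report the treatment x characteristic coefficient, which pools the baseline and 12-week rows.

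What is at stake is the size of the reported modification. C4 and D8 say that finding who benefits most, and learning effect sizes, are meant to shape a larger multi-centre trial. A planner who took the coefficient at face value would use a subgroup difference about half as large as the data support. The same specification is carried to the Aim 2 imaging outcomes.

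A smaller matter is the HbA1c source. Recruitment (D2b) now reaches beyond the registry cohort to community talks, advertisements, mailing lists and clinics, so a registry-defined value may not be obtained in the same way for everyone.

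**Working it through.** **Inputs from D7.** The test is "conducted with a 2-sided 5% significance level". "we have 80% power to detect an improvement in the HBOT group of 0.224" and "The predicted mean change in the sham group from baseline to 12 weeks is -0.02" together give a difference of 0.224 + 0.020 = 0.244. "Assuming an SD of 0.50 in both the sham and HBOT groups" gives the SD. There are 67 evaluable per arm, with 13% dropout and 77 enrolled per arm.

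**Reproducing the plan's figure.** n = 2(1.96 + 0.842)² x 0.50² / 0.244² = 65.9, so 66 by the normal approximation. The t-test version gives 66.9, so 67, with power 80.1%. Also 67/0.87 = 77.01, against 77 enrolled. The plan states no figure for the subgroup analysis.

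**Algebra.** Let C be the characteristic, B the baseline value, W = 0 at baseline and 1 at 12 weeks, and T the arm. The model as written has mean

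b0 + b1·B + b2·W + b3·T + b4·W·T + b5·C + b6·T·C.

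- The between-arm difference in change is b4 whether C = 0 or C = 1.
- b6 is the modification averaged over rows. Randomisation makes it 0 at baseline in expectation, and it is d at 12 weeks.
- Complete data: b6 = (0 + d)/2 = 0.50d.
- With 13% missing at 12 weeks, the later rows are 0.87/(1 + 0.87) = 0.465 of the total. The subject variance was estimated as zero in nearly all simulated fits, so rows carry equal weight and b6 is about 0.465d.

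**Simulation.** The assumptions, which are not in the documents, are a modification d of 0.244 (as large as the whole planned effect) or 0.488, strata 50:50, and a baseline/12-week correlation of 0.5, 0.7 or 0.9. The SD of change is 0.50, the random subject intercept is fitted by REML, and cluster effects are left out.

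At 5,000 per arm, d = 0.244, correlation 0.7:

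| Data | As written | With three-way term | 12-week ANCOVA |
|---|---|---|---|
| Complete | 0.123 | 0.247 | 0.245 |
| 13% missing | 0.114 | 0.245 | 0.246 |

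At trial size, correlation 0.7, 600 runs per row, showing mean estimate (mean SE) and rejection rate:

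| d | Data | As written | With three-way term | 12-week ANCOVA |
|---|---|---|---|---|
| 0.244 | 67 per arm, complete | 0.120 (0.085), 27.0% | 0.241 (0.167), 31.8% | 0.240 (0.161), 30.5% |
| 0.244 | 77 per arm, 13% missing | 0.108 (0.079), 28.8% | 0.230 (0.156), 33.5% | 0.233 (0.161), 31.7% |
| 0.488 | 67 per arm, complete | 0.243 (0.086), 81.8% | 0.486 (0.167), 83.5% | 0.487 (0.160), 85.3% |
| 0.488 | 77 per arm, 13% missing | 0.226 (0.081), 82.3% | 0.487 (0.156), 85.0% | 0.487 (0.161), 84.7% |

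For both values of d and at every correlation, the ratio of the as-written estimate to the 12-week ANCOVA was 0.500 with complete data and 0.463 to 0.468 with 13% missing. The standard error shrinks in about the same proportion, which is why the test moves little.

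**Precision.** With four cells of 33.5 and unadjusted change, SE = 0.50 x √(4/33.5) = 0.173. Power at d = 0.244 is Φ(0.244/0.173 − 1.96) = 29%. The modification detectable with 80% power is 2.80 x 0.173 = 0.48.

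**The case against.** The strongest reply is that the sentence is a short description. It says the models resemble those of Aims 1 and 2, its purpose is to study improvement, and the authors clearly know the three-way structure because they write it out for the baseline value. The intended model may therefore be right. That is fair as to intent. But the list of added terms is explicit, it stops at a two-way interaction, and the contrast with the baseline-value test in the same section makes the omission visible. An analyst following the text would fit the attenuated model.

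The reply also limits the scope, and these limits stand. The analysis is exploratory. Sign and test are nearly unchanged. D6 also has exploratory trend models that use post-baseline visits only, and there treatment x characteristic recovers a sustained modification in full (0.400 for a true 0.40 in simulation). Low precision is a larger limit on these subgroup results than the missing term.

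On HbA1c, a reader might infer that the subgroup analysis depends on the registry value and that participants recruited elsewhere will lack one. The documents do not support either. Registry HbA1c is one of three examples. D2b expects many participants from the IDCD cohort, and E.1.a provides for HbA1c from HMO charts. Nor can the information lost by cutting at 7 be put in figures, because the distribution of HbA1c is not given; the efficiency of a median split does not apply to this cut.

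**Conclusion.** The point holds for the baseline/12-week model fitted as the text specifies it. The treatment x characteristic coefficient is 0.50 of the true modification with complete data and about 0.47 with 13% missing at 12 weeks. This rests on randomisation (no modification at baseline) and on two occasions per participant. The ratio did not depend on the assumed size of the modification or on the baseline/12-week correlation.

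A reader might go further and infer that subgroup significance tests are invalid, that every subgroup estimate in the plan is halved, or that the efficacy result is biased. None of these follows. Rejection rates differ by a few percentage points, models on follow-up visits only are unaffected, and the primary analysis does not contain the term. What is wrong is the size of the reported subgroup effects, and that size is what the next trial's design would draw on.

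**What to change.** Replace the list of added terms in D6 by one of these two:

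- the baseline/12-week model with time x treatment x characteristic and all lower-order terms, as D6 already does for the baseline value, reporting the three-way coefficient as the effect modification; or
- an ANCOVA of the 12-week value with baseline as covariate, plus treatment, characteristic and treatment x characteristic, reporting the last coefficient.

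Both recover the full effect. The 12-week ANCOVA is the safer choice here. With no true modification and 13% missing, the three-way test rejected in 8.3% to 9.2% of simulated trials at a nominal 5%, against 5.3% to 6.2% for the ANCOVA. Those runs had a random subject intercept and no cluster effect. Apply the same wording to the imaging outcomes, and report estimates with 95% confidence intervals in view of the low precision.

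As a minor addition, define HbA1c from one uniform baseline source, namely the trial's baseline blood sample, and enter it as continuous. The cut at 7 can stay for display. D2K names HbA1c only as an example, so the sponsor should confirm that it is assayed at baseline for all participants.

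The cost is SAP wording, with no added visit or procedure provided that assay is confirmed.

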Aims 2a and 2b: CBF and cerebral glucose utilization will be analyzed with a similar strategy to Aims 1a and 1b except that there will be no 6 month assessment. Mixed effects ANCOVA models will be used to compare changes in these outcome measures from baseline to 12 weeks following treatment, and, as exploratory analyses, linear mixed effects models will be used to assess relationships between treatment group (fixed effect) and the longitudinal trend (random intercept and slope for each subject) in MRI-ASL and FDG-PET outcome measures, assessed at 12-weeks and 12 months following treatment. Vascular effects of HBOT vs. Sham: Since CBF derived from ASL perfusion may represent combined effects of neural metabolism and vascular effects, a secondary mixed effects ANCOVA model (similar to Aim 2b) of vascular changes from baseline to 12 weeks as measured by ASL CBF will adjust for neural metabolism derived from FDG-PET.

Aim 3: Outcome measures (changes in CBF and cerebral glucose utilization) identified as having significant associations with treatment group in Aims 2a and 2b will be further explored as mediators of the relationship between treatment group and the change in cognition. To ensure that measurement of mediator

variables precedes measurement of cognition, we will define the outcome as the change in cognition from baseline to 12 months, and the mediators as changes in CBF and cerebral glucose utilization, from baseline to 12 weeks. The product of coefficients approach will be used within a multiple mediator modeling framework to provide point estimates of both the specific indirect effect (i.e. the effect of treatment group on the change in cognition from baseline to 12 months via a mediator among other mediators in the model) and the total indirect effect (i.e. the sum of specific indirect effects for all mediators in the model). The bootstrapping method⁹³ will be used in each multiple mediator model to compute bias-corrected standard errors (and 95% confidence intervals) for the specific and total indirect effect point estimates.

D7. Power Analysis and sample size justification

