Involvement. The T2D subjects involved in this RCT will participate in neuropsychological assessments involving a clinical/diagnostic interview and paper and pencil tests. In addition, they will be interviewed in a risk factor inventory in which basic demographic, some medical information, and past behaviors (e.g. smoking, physical activity) will be assessed. In addition, subjects will go through an MRI examination and a PET scan. Subjects will be also asked about their activities of daily living and instrumental activities of daily living. Only subjects who have a diagnosis of T2D and a diagnosis of MCI will participate in the study. Subjects will be randomized to HBOT or sham. Both groups will be treated in the oxygen chamber for 60 sessions, 5 times/week, 90 minutes each session and will receive 100% oxygen. The HBOT group will have 2.0 ATA during the treatment while the sham group will receive 1.1 ATA during the first and last five minutes of the 90-minute sessions. All other conditions and assessments will be identical for the two groups. All assessments will be performed at baseline (before treatment), at 12 weeks (immediately after treatment) and at 12 months (to assess maintenance of HBOT effects in the long term). At 6 months, only the cognitive assessments will be assessed. Upon informed consent, subjects' long term diabetes characteristics (such as HbA1C, duration of disease, anti-diabetic medication status, and hypertension status) will be given by the subject who will provide the investigating team with the computerized medical chart from the HMO.

Characteristics. Eligibility criteria are summarized in **Table 1, section D2a** of the application. This study will consist of 154 elderly subjects (>65 years of age) who have T2D and a diagnosis of MCI (both amnestic and non-amnestic). Subjects must have at least one informant and must speak fluent Hebrew for the neuropsychological assessment. Subjects may not have a brain disease that might affect cognition such as schizophrenia or Parkinson's disease, they may not have epilepsy, inner ear disease, or claustrophobia. Subjects cannot be receiving cholinesterase inhibitors and cannot have an indication for HBOT, such as diabetic foot, since then they cannot be randomized to the sham group. There are no inclusion or exclusion criteria on the basis of sex, race, ethnicity, religion, or any other minority affiliations. Within the elderly, Israel is primarily a

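### The only analysis written out for the 12-month MRI and PET is a two-visit post-treatment trend, which does not suit the maintenance question; a 12-month contrast with baseline is left to inference

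*Combined protocol and SAP*

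**What the plan says.** MRI ASL and FDG-PET are scheduled at baseline, at 12 weeks and at 12 months, with no imaging at 6 months (Table 2; D2c; D2j for ASL). Section E.1.a gives the reason for the last round: assessments are repeated "at 12 months (to assess maintenance of HBOT effects in the long term".

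Under Aims 2a and 2b, D6 first says that imaging will be handled much as cognition is under Aims 1a and 1b, less the 6-month visit. It then writes out two analyses across visits:

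- a mixed-effects ANCOVA of change from baseline to 12 weeks;
- an exploratory linear mixed model relating treatment group to "the longitudinal trend (random intercept and slope for each subject", fitted to the values "in MRI-ASL and FDG-PET outcome measures, assessed at 12-weeks and 12 months following treatment".

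A further ANCOVA, which adjusts CBF for FDG-PET, also covers baseline to 12 weeks. The mediation analysis uses the 12-week imaging changes.

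For cognition, D6 does more. It states secondary ANCOVAs at 6 and 12 months, a trend model over three follow-up visits, and the test for that model: the treatment-by-time interaction.

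**The concern.** The trend model appears to have been carried over from cognition, where there are three post-treatment visits, to imaging, where there are two. Two things change.

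First, two points per subject cannot separate a random intercept, a random slope, their covariance and a residual variance.

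Second, the slope between 12 weeks and 12 months starts when treatment ends. If HBOT raises CBF by 12 weeks and the gain holds, the arms run parallel and the interaction is zero. If the gain is lost, the interaction is large and goes against HBOT. The best long-term result therefore gives a null trend test, and a significant result may mean that the benefit has gone.

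At stake is whether a third round of MRI and PET, scheduled to assess maintenance, has a stated between-arm estimate of the 12-month effect. If it is left to inference, whether and how to run it could be decided after the data have been seen.

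**Working it through.** **Inputs (D7, Table 3).** "Power calculations are based on two-sample t-tests and are conducted with a 2-sided 5% significance level". For CBF: "Assuming a mean change in CBF velocity of -0.45 in the Sham group and an SD of 5.6 in both groups", and with "67 patients per arm we have 80% power to detect an improvement in the HBOT group of 2.28, an effect size of 0.49". For glucose utilization: "assuming a mean change in the sham group of -0.08 and an SD of 4.40 in both groups", with an HBOT change of 2.065. Enrolment: "anticipated dropout rate of 13%, we plan to enroll 77 patients per group for a total of 154 patients".

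**The plan's own figures.**
- CBF: difference 2.28 + 0.45 = 2.73; d = 2.73/5.6 = 0.4875.
- Glucose utilization: difference 2.065 + 0.08 = 2.145; d = 2.145/4.40 = 0.4875.
- Noncentrality at 67 per arm: 0.4875 × √(67/2) = 2.82, which gives t-test power of 0.800. The stated 80% reproduces.
- Enrolment: 67/0.87 = 77.01, against the stated 77. This agrees apart from rounding.

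**Covariance parameters.** Two visits supply three moments: two variances and one covariance. Correlated random effects plus residual need four parameters. With times coded 0 and 1, intercept variance a, covariance c, slope variance b and residual variance s:
- var(first visit) = a + s
- cov = a + c
- var(second visit) = a + 2c + b + s

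Two different parameter sets give the same matrix:

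| a | c | b | s | var 1 | cov | var 2 |
|---|---|---|---|---|---|---|
| 20 | 0 | 4 | 8 | 28 | 20 | 32 |
| 24 | −4 | 12 | 4 | 28 | 20 | 32 |

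No data at these two visits can tell them apart. With three visits there are six moments for four parameters, and the model is identified. That holds for cognition at 12 weeks, 6 months and 12 months, and would hold for imaging if baseline were a visit.

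**The fixed effect.** With two visits and complete data, the treatment-by-time test is equivalent to a t-test on the 12-week-to-12-month change. In one simulated data set with the effect fully maintained, the coefficient was 0.228 (SE 1.291) both with the random slope and with a random intercept alone. Non-identification therefore affects the variance components and not this estimate.

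**What the interaction tests.** The expected arm difference in CBF is 2.73 at 12 weeks and 2.73 × k at 12 months, where k is the fraction retained. The trend contrast is 2.73 × (k − 1):
- k = 1: 0
- k = 0.5: −1.365
- k = 0: −2.73

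**Rejection rates.** These come from a simulation with 67 per arm and 4,000 replicates per setting. Three assumptions are not in the documents: equal variances and correlations across the three visits, a visit correlation of 0.5 or 0.7, and a change SD of 5.6 at 12 months as well.

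| Retained at 12 months | Trend interaction | Baseline-to-12-month change | 12-month ANCOVA |
|---|---|---|---|
| All | 4–6% | 79–80% | 86–90% |
| Half | 28–30% (against HBOT in expectation) | 28–29% | 31–36% |
| None | 80% | 5% | 5% |

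The 5% in the first row does not depend on the correlation: the expected contrast is zero, so the test rejects at its nominal level.

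**Range for the 80%.** D2g reports dropout of 5% to 20% in the team's earlier HBOT studies. That leaves 77 × 0.95 = 73 or 77 × 0.80 = 61 per arm. The t-test power for a fully maintained 2.73 is then 83% or 76% with SD 5.6. If the 12-month change SD were 25% larger (7.0, an illustrative assumption; d = 2.73/7.0 = 0.39), power at 73, 67 and 61 per arm would be 65%, 61% and 57%.

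**The case against.** The strongest reply is that the paragraph already covers the 12-month effect. It models imaging on cognition and removes only the 6-month visit. The cognitive plan has ANCOVAs at 6 and 12 months, so a 12-month imaging ANCOVA remains by reference. This is a plausible reading, and a reader who infers that the trend model is the only planned 12-month analysis, or that maintenance goes unanswered, goes further than the text allows. What stands is narrower: the cognitive sentence is worded for cognitive assessments, and the imaging paragraph restates the 12-week ANCOVA and the trend model but not the 12-month ANCOVA.

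A reader might also call the trend model not estimable. That is too strong. D6 does not say that the random effects are correlated. If they are independent, three parameters meet three moments: with times 0 and 1, intercept variance = cov, residual = var 1 − cov, and slope variance = var 2 − var 1. Even with correlated effects, the interaction is estimated. D6 also excludes patients without a baseline value from all analyses, which may suggest that baseline enters somewhere; but the trend sentence lists only the two later visits.

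Nor would a maintained effect vanish from every term. In the simulated fit above, the group term was 2.179 (p = 0.024). The plan does not name that term as the test, however. Read beside the 12-week ANCOVA, a flat trend after an early gain is what maintenance looks like. But a non-significant interaction does not establish maintenance, and it gives no estimate of the 12-month effect.

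Finally, the trend models are labelled exploratory and the study is a self-described pilot. Both limit the impact.

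**Conclusion.** The point holds in limited form. The only imaging analysis written out that uses the 12-month scans as outcomes has a random-effects structure that two visits cannot support if the effects are correlated (four parameters, three moments). Its interaction answers whether the arms diverge after treatment, and not whether the effect against baseline is still there at 12 months.

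Under full maintenance of the planned effect, the interaction rejects at about 5%, against about 80% for a contrast of baseline-to-12-month change. The 80% assumes that the 12-week SD and 67 per arm carry over; the documents give neither a 12-month SD nor 12-month retention. The parameter count assumes correlated random effects and nominal visit times. Reading the interaction as the imaging trend test assumes that the test stated for cognition applies.

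The documents do not support saying that maintenance is left without any analysis. They support saying that its estimate is left to inference. The 12-week imaging ANCOVA, the primary cognitive outcome and the sample size are unaffected.

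**What to change.** In D6, Aims 2a and 2b, name the maintenance analysis: a baseline-adjusted HBOT-sham contrast at 12 months for CBF and for FDG-PET, each with a 95% CI. One way is a single model per outcome with baseline, 12 weeks and 12 months as responses, visit as a categorical factor, treatment-by-visit terms, an unstructured within-subject covariance and the cluster random effect already planned. It gives the difference in change from baseline at 12 weeks (main) and at 12 months (maintenance). A sentence that states the 12-month ANCOVA outright would also close the main gap.

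If the trend model is kept, drop its random slope or include baseline as a visit. Report the 12-week-to-12-month contrast only as a description of waning.

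The cost is SAP wording. The scans are already scheduled, and no further patients or visits are needed.
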